
In addition, it is extremely important to evaluate whether the reduction of the weekly dose of HCQ after a long period of use of this therapy would be able to maintain inhibition of TLR-7 and -9.

Objectives primary:

- Compare the frequency of outbreaks of disease activity (SLE and jSLE) in patients using standard dose (HCQ 400 mg/day) vs. patients with reduced dose (HCQ 400 mg/3X week) and its correlation with blood and saliva levels of the drug. Secondary: - Compare frequency of retinopathy in patients using standard dose (HCQ 400 mg/day) vs. patients with reduced dose (HCQ 400 mg/3X week) and its correlation with HCQ blood levels.

- Verify a possible longitudinal correlation of HCQ concentrations with the production of interferon-alpha and TNF by plasmacytoid dendritic cells.

- Correlate blood and salivary levels of HCQ and its metabolites in patients with SLE and JSLE with adherence to this treatment.

- Correlate functional and structural damage of the retina, evaluated by central visual field examination (campimetry) and SD-OCT measurements, with segmentation of the outer layer of the retina (pigment epithelium).

- Establishment of a pharmacokinetic-pharmacodynamic model of hydroxychloroquine dose reduction in patients with SLE.

NUMBER OF INDIVIDUALS

Total number of patients required for the study= 256 (SLE and JSLE).

STUDY DESIGN

Randomized controlled prospective study of non-inferiority of one year of follow-up of patients with SLE and JSLE in remission with HCQ use (stable dose of 400 mg/day for at least five years).

Patients will be randomized into two groups: no daily dose reduction group (HCQ 400 mg/day) and reduction group (HCQ 400 mg/day - 3X week). Patients will be evaluated for the activity of the underlying disease in a "blind" way. HCQ concentrations will be measured at the entrance, 6 months and 12 months after.

The groups will be compared for episodes of disease activity (clinical and laboratory parameters). The production of interferon-alpha and TNF by plasmacytoid dendritic cells will be evaluated in the same period in a subgroup of patients.

The following indexes will be used to assess disease activity:

- SLE and JSLE: SLEDAI-2K (Gladman et al., 2002) and active disease randomly defined as SLEDAI-2K \geq 6.

- Renal activity: BP, urine type I, protein and creatinine in an isolated urine sample, serum creatinine, C3, C4, anti-dsDNA, according to the recommendations of the ACR (Hahn et al., 2012).

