Adherence will be assessed by the MASRI questionnaire applied by a pharmacist not directly involved in patient care (Koneru et al., 2007).

The following clinical, laboratory and treatment data will be evaluated in the groups (active disease and inactive disease): age, sex, race, weight, height, BMI, ideal weight; disease time, time of HCQ use, adherence to treatment; smoking; use and dose of prednisone, methotrexate, azathioprine, mycophenolate mofetil, cyclophosphamide, non-hormonal anti-inflammatory drugs; urinary protein/creatinine ratio; serum creatinine; blood concentrations of HCQ by HPLC; specific adverse events.

- Complete ophthalmologic assessment (at the entrance and at the end of the study), including campimetry and SD-OCT measurements, with segmentation of the outer layer of the retina (pigmentary epithelium).

- The production of interferon-alpha and TNF-alpha by plasmacytoid dendritic cells will be evaluated in vitro using mononuclear cell preparations isolated from peripheral blood from a random sample of the same number of consecutive patients with active and inactive SLE. The cells will be stimulated with the TLR-9 agonist, Oligodeoxynucleotide S CpG (ODN CpG-A)-2216 and with the TLR-7 agonist, imiquimod. The percentage of monocytes, B cells, dendritic cells and natural killers (NK) in the PBMC fraction will be determined by the phenotypic characterization of these cell subpopulations by flow cytometry using monoclonal fluorochrome-conjugated antibodies. Intracellular detection of IFN-alpha and TNF-alpha in plasmacytoid dendritic cells will also be performed by flow cytometry and specific monoclonal antibodies (Sacre et al., 2012).

- Establishment of a pharmacokinetic-pharmacodynamic model of hydroxychloroquine use with two groups of 5 patients: one with 5mg/kg/day daily and another 5mg/Kg/day 3 times a week. On inclusion both will be on hydroxychloroquine use for at least 6 months and should have the stable level of the drug (> 1000ng/mL).

Outcomes: assessment on days 0 and 120 days.

a) Worsens no SLEDAI -2K. Change in SLEDAI-2K evaluating activity criteria from 0-105 in 9 organs and 24 items (clinical and laboratorial). The increase represents clinical/laboratory worsening of the disease.

b) Cytokine measurement. Plasma levels of TNF- α and IFN-1 will be determined by Luminex MAP (EMD Millipore Corporation®). Plasma samples will be stored at -80oC until use.

TARGET POPULATION

Inclusion criteria:

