- LES and jSLE (ACR criteria) (Hochberg, 1997);
- use of HCQ at a dose of 400 mg/day for at least 3 years.

Exclusion criteria:

- alcoholism;
- renal dialysis;
- concomitant infectious process;
- acute and chronic liver diseases;
- concomitant use of some drugs that interact with HCQ (cimetidine, antacids, digoxin, aminoglycosides, penicillin, neostigmine, pyridostigmine).

RELEVANT METHODS - Ophthalmological assessment: central visual field examination (campimetry) and SD-OCT measurements, with segmentation of the outer layer of the retina (pigmentary epithelium).

- Blood levels of HCQ will be determined by HPLC MS/MS (Munster et al., 2002).

- Pharmacokinetic analysis: The pharmacokinetic parameters of hydroxychloroquine will be calculated in the 24 h dose range based on the total plasma concentration versus time curves. The Winnonlin program, version 4.0 (PharsightCorp., Mountain View, California, USA) and the Non-linear mixed effect level (NONMEM) program will be employed. The area under the plasma concentration curve versus time will be calculated in the 24-h dose interval by the trapezoid method on days 0 and 120. The apparent total clearance (CIT/F) will be obtained through the equation: $CIT/F = Dose/AUC_{0-24}$. The apparent distribution volume (Vd/F) will be calculated by the standard software equation. The hydroxychloroquine-free concentration will be determined by the dosage in saliva. The PK-PD analysis will be performed using as pharmacokinetic parameters the total and free plasma concentrations of hydroxychloroquine and, as a pharmacodynamic parameter, we will use the clinical/laboratory indices obtained by the evaluation of SLEDAI-2K (American College of Rheumatology). The PK-PD model will be developed using the non-linear mixed effect level (NONMEM).

- Others, the same as described in subproject 1A.

Safety

Monitoring of outbreaks of inflammatory activity (flare) and identification of retinopathy.

WITHDRAWALS

Signs of retinopathy.

ORIGINALITY WITH IMPACT on

Healthcare

To date, there is no study demonstrating that the reduction of HCQ dosage after tissue depot caused by a prolonged time of use of the drug can be safely performed in SLEJ and SLE, without increasing the number of outbreaks of inflammatory activity.

The expected care impact is a reduction of severe ophthalmologic event with the reduction of the HCQ dose and the expansion of the time of use of the drug that has a direct impact on the control of disease activity.

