- The production of interferon-alpha and TNF-alpha by plasmacytoid dendritic cells will be evaluated in vitro using mononuclear cell preparations isolated from peripheral blood from a random sample of the same number of consecutive patients with active and inactive SLE. The cells will be

stimulated with the TLR-9 agonist, Oligodeoxynucleotides CpG (ODN CpG-A)-2216 and the TLR-7 agonist, imiquimod. The percentage of monocytes, B cells, dendritic cells and natural killers (NK) in the PBMC fraction will be determined by the phenotypic characterization of these cell subpopulations by flow cytometry using monoclonal fluorochrome-conjugated antibodies. Intracellular detection of IFN-alpha and TNF-alpha in plasmacytoid dendritic cells will also be performed by flow cytometry and specific monoclonal antibodies (Sacre et al., 2012).

TARGET POPULATION

Inclusion criteria:

- SLE (ACR criteria) (Hochberg, 1997);
- without using HCQ at a dose of 400 mg/day for at least 6 months.

Exclusion criteria:

- alcoholism;
- renal dialysis;
- concomitant infectious process;
- acute and chronic liver diseases;
- concomitant use of drugs that interact with HCQ (cimetidine, antacids, digoxin, aminoglycosides, penicillin, neostigmine, pyridostigmine).

RELEVANT METHODS

See subproject 1A.

Safety. Monitoring of adverse events and outbreaks of inflammatory activity (flare).

ORIGINALITY WITH IMPACT ON ASSISTANCE

There are no studies in SLE that assess how long after the start of treatment is necessary to achieve adequate HCQ blood and salivary level, nor whether a higher initial dose (attack) could anticipate these levels to provide an earlier clinical/laboratory response without increasing adverse effects.

The expected impact would be that the dosage of HCQ levels would allow to perform a control of the inflammatory activity of the disease earlier and safely.

ADVANCES IN MECHANISMS To compare the inhibitory action of different doses of HCQ in TLRs -7 and -9 and its relevance to the immunomodulatory action of the drug.

SAMPLE SIZE

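### The dendritic-cell substudies in randomised trials 1B and 1C reuse 1A's sampling by disease activity and leave arm, time of classification and size unstated, which does not fit their dose and longitudinal questions

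*Combined protocol and SAP*

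**What the plan says.** The protocol's first subproject (1A) is cross-sectional and compares patients with and without disease activity. For the plasmacytoid dendritic-cell work it takes cells "from a random sample of the same number of consecutive patients with active and inactive SLE". The same sentence stands in the study design of 1B (standard v reduced dose) and of 1C (standard v attack dose). In none of the three does it mention a number or a time of classification, and in 1B and 1C it does not mention arm.

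What 1B and 1C want from these cells:

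- **1B, Background:** a question about the receptors TLR-7 and TLR-9, namely if "the reduction of the weekly dose of HCQ after a long period of use of this therapy would be able to maintain inhibition". Its paragraph on advances in mechanisms presents the answer as support for a lower dose.
- **1B, secondary objectives:** "Verify a possible longitudinal correlation of HCQ concentrations with the production of interferon-alpha and TNF by plasmacytoid dendritic cells".
- **1B, Study design:** cytokine production "will be evaluated in the same period in a subgroup of patients" as the follow-up. HCQ is measured at entry, 6 months and 12 months.
- **1C, Advances in mechanisms:** "To compare the inhibitory action of different doses of HCQ in TLRs -7 and -9". The study design also compares the arms on inflammatory cytokines and TLR-7/-9 expression.
- **1C, secondary objectives:** a correlation of HCQ concentration with cytokine production and disease activity.

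On who can be active in 1B, the study design describes "patients with SLE and JSLE in remission with HCQ use (stable dose of 400 mg/day for at least five years"), and the same section has "active disease randomly defined as SLEDAI-2K" of 6 or more. The 1B inclusion list gives only the ACR criteria and "use of HCQ at a dose of 400 mg/day for at least 3 years"; remission is not in it.

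The statistical paragraphs of 1B and 1C describe no dendritic-cell analysis by arm.

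**The concern.** A rule that balances active against inactive patients suits a study that compares those two groups. In 1B and 1C the mechanistic question is about dose, and a dose question is best served by a sample balanced by arm and taken before treatment can change anything.

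The wording looks carried over from 1A. In 1C the list of clinical data to be collected was adapted to the two dose groups, but the dendritic-cell sentence was not. In 1B even that list still names active and inactive disease as its groups.

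Three things are at stake:

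1. In 1B, if patients enter in remission, the active half can come only from those who flare after randomisation. Flare is the primary outcome, so the subsample is selected on it.
2. A patient chosen because of a flare may have no baseline cells. The methods describe cells being isolated and stimulated. Frozen storage is stated for the HCQ blood samples and for plasma, but not for these cells. The longitudinal correlation listed in 1B needs repeated measurements on the same people.
3. Balance between arms is left to chance, and in 1B it also depends on the flare rates.

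Random selection and consecutive selection are also different methods, and the sentence asks for both.

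**Working it through.** **Inputs from the plan (1B, Sample size).** Success at one year on the standard dose 84%; margin 12 points; alpha 5%; power 80%; losses 10%; 128 per arm. The substudy has no stated size, cytokine SD or target difference, so it has no figure of its own to reproduce.

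**Step 1: reproduce 128 per arm.** Take 84% success in both arms and a one-sided 5% test.

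n = (1.645 + 0.842)² × 2 × 0.84 × 0.16 / 0.12² = 6.18 × 0.2688 / 0.0144 ≈ 115.4, so 116 per arm.

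With 10% losses: 116 × 1.1 = 127.6, so 128 (116 / 0.9 gives 129). The plan's figure is consistent with equal success rates of 84%.

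**Step 2: who is active in 1B.** Assume that a patient without success is active by the SLEDAI-2K rule, and take about 115 evaluable per arm. Expected active patients on the standard dose: 115 × 0.16 = 18.4.

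| Success on reduced dose | Active, standard | Active, reduced | Reduced-dose share of active | Reduced-dose share of inactive |
|---|---|---|---|---|
| 84% | 18.4 | 18.4 | 50% | 50% |
| 76% | 18.4 | 27.6 | 60% | 47.5% |
| 72% (margin) | 18.4 | 32.2 | 64% | 46% |

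At 84% in both arms, 16% of patients fill 50% of the subsample. An active patient is then 84/16 = 5.25 times as likely to be sampled as an inactive one. At 84% v 72% the reduced arm's expected share of the subsample is (63.6% + 46.2%) / 2 ≈ 55%.

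**Step 3: how much bias.** In a simulation the cytokine response has SD 1, the true arm difference is 0, 0.3 or 0.5 SD, and the log-odds of flare rise by 0.5 or 1.0 per SD of cytokine. These associations are assumptions. Equal numbers of active and inactive patients are drawn and the crude arm difference is taken.

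- Success 84% v 84%: estimates 0.000 and −0.002 (true 0), 0.303 and 0.301 (true 0.3), 0.496 and 0.500 (true 0.5). There is no bias beyond simulation noise.
- Success 84% v 72%: estimates 0.027 and 0.036 (true 0), 0.330 and 0.335 (true 0.3), 0.522 and 0.533 (true 0.5). The bias is 0.02 to 0.04 SD.

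**Step 4: chance imbalance between arms.** The sizes are assumptions. If arm is ignored and patients are drawn without replacement from two equal arms:

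| Drawn from | Subsample | Chance of 60:40 or worse | Chance of 65:35 or worse |
|---|---|---|---|
| 256 (1B) | 20 | 49% | 24% |
| 256 (1B) | 40 | 23% | 6% |
| 96 (1C) | 20 | 45% | 21% |
| 96 (1C) | 40 | 15% | 2% |

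The cost of 13:7 against 10:10 in the standard error of an arm difference is √(1/13 + 1/7) / √(1/10 + 1/10) = 0.4688 / 0.4472 = 1.048, about 5%.

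**Step 5: 1C.** Patients are starting HCQ and no remission requirement is stated, so active and inactive patients can both be present at entry. If activity is classified at entry, the rule is stratification on a baseline variable and does not bias the arm comparison. If it is classified later, the selection problem of 1B applies. The protocol does not say which.

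**The case against.** The strongest reply is that the listed dendritic-cell objectives in both trials are correlations with HCQ concentration, and a correlation does not need sampling by arm. In 1C the objective also names disease activity, so having both active and inactive patients serves it. This stands in part. 1B's dose question appears in its background and mechanisms text and not among its objectives. But 1C states its dose comparison outright, and 1B's correlation is longitudinal, which sampling after a flare does not support.

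A reader might infer that the arms cannot be validly compared. The documents do not support that. Both arms would be in the sample, recorded sampling fractions would allow weighting, and the simulated bias is small, and nil at the equal rates behind the 128 per arm. Chance imbalance in arm sizes is a small loss of precision and not a bias.

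A reader might also infer that 1B can have no active patients at entry. Remission is stated only in the design paragraph, is not defined there, and is absent from the inclusion list. Nor does the plan say that the active/inactive draw takes place at baseline.

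The clash between random and consecutive may be a translation slip. Finally, the substudy feeds no primary endpoint, sample size or safety decision, which limits the severity.

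**Conclusion.** The concern holds in a limited form. The sampling rule in 1B and 1C is that of a cross-sectional study. It leaves arm, time of classification and size unstated, and does not match the dose question in either trial or the longitudinal objective in 1B.

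In 1B, if the remission description governs, the rule selects on the primary outcome: about 16% of patients would supply half the subsample, with no assured baseline cells. In 1C it is harmful only if activity is classified after randomisation; otherwise what remains is that balance by arm is unprotected.

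The numerical harm is probably small: a bias of 0 to about 0.04 SD under the assumed associations and flare rates, and about 5% in the standard error for a 13:7 split of an assumed 20 patients. It would be wrong to conclude that the comparison is impossible, or that 1C shares 1B's problem whatever the timing. This is a cheap improvement to an exploratory substudy, of lower severity.

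**What to change.** In 1B and 1C, replace the carried-over sentence:

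- Draw the subsample at randomisation, with equal numbers chosen at random from each arm, and state the number. In 1C the draw may also be stratified by activity at entry.
- Measure the same patients at each planned time, including baseline.
- Add an analysis that compares the arms adjusting for the baseline cytokine response, and keep the listed correlation with HCQ level in the same patients.
- Name one selection method. With a random draw, the reference to consecutive patients goes.
- In 1B, reconcile the remission description in the study design with the inclusion list. The required duration of HCQ use also differs between these two places and needs reconciling.

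The cost is protocol wording. No extra patients are needed and the number of assays can stay as intended. The downside is fewer active patients for an active v inactive comparison in 1B and 1C, which 1A already provides.

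### Subproject 1B PK-PD substudy: Dose/AUC0-24 is not a valid clearance for the three-times-weekly group at day 120

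*Combined protocol and SAP*

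**What the plan says.** Subproject 1B, Study Design, sets up a PK-PD substudy in two groups of 5 patients, "one with 5mg/kg/day daily and another 5mg/Kg/day 3 times a week", assessed on days 0 and 120. On the patients' state at entry it says "On inclusion both will be on hydroxychloroquine use for at least 6 months", with a stable level above 1000 ng/mL. It does not give the dosing frequency before day 0. The trial's own inclusion criterion is "use of HCQ at a dose of 400 mg/day for at least 3 years".

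Under Relevant Methods, one pharmacokinetic rule serves both groups. The AUC "will be calculated in the 24-h dose interval by the trapezoid method on days 0 and 120". Then "The apparent total clearance (CIT/F) will be obtained through the equation" CL/F = Dose/AUC0-24. Dose is not defined for the three-times-weekly group, and the text does not say whether day 120 is a dosing day. For volume, "The apparent distribution volume (Vd/F) will be calculated by the standard software equation".

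Two further statements limit the damage. WinNonlin is named, and "the Non-linear mixed effect level (NONMEM) program will be employed" as well. Also, "The PK-PD analysis will be performed using as pharmacokinetic parameters the total and free plasma concentrations of hydroxychloroquine", so the PK-PD model takes measured concentrations as input and not CL/F.

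The Introduction and the Justification of Subproject 1C both give the half-life of antimalarials as about 40 days.

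**The concern.** Dose divided by the AUC over an interval equals CL/F only if that interval is the dosing interval and drug input balances elimination over it. The daily group meets both conditions. The three-times-weekly group at day 120 does not: a 24 h window is shorter than the time between its doses, and blood levels are still falling if the patients came from daily dosing.

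Followed as written, the plan would report a day 120 clearance for the reduced-dose group that differs from its own day 0 value and from the daily group, with no change in true clearance. Dose reduction is the subject of this secondary objective, so such a shift could be read as altered elimination on the lower dose. A Vd/F calculated from this CL/F would carry the same error.

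**Working it through.** The plan gives no clearance figure, so there is none to reproduce. The check asks what Dose/AUC0-24 would return if true clearance did not change.

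**Inputs from the documents**
- The same amount on each dosing day, on 7 of 7 days or 3 of 7 days. The ratio of average daily input is f = 3/7 = 0.4286.
- Half-life of about 40 days.
- AUC window of 24 h, on days 0 and 120. Day 120 is 120/40 = 3 half-lives after day 0.

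**Assumptions**
- Linear one-compartment kinetics and constant true CL/F.
- Daily dosing to steady state before day 0. This fits the inclusion criterion and the dose-reduction objective but is not stated for the substudy.

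**Closed form.** The 24 h exposure t days after the change, relative to the daily steady state, is

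R(t) = f + (1 − f) × 2^(−t/40)

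R(120) = 3/7 + (4/7)/8 = 0.500

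- Dose read as the single dose: apparent/true CL/F = 1/0.500 = 2.00.
- Dose read as the weekly-average daily dose: 0.4286/0.500 = 0.857, i.e. 14.3% too low.

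**Dose-by-dose superposition at day 120**, with doses on days 0, 2 and 4 of the week and all seven alignments of that pattern:

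| Half-life | Single dose | Weekly average |
|---|---|---|
| 30 days | 2.12–2.21 | 0.91–0.95 |
| 40 days | 1.98–2.04 | 0.85–0.87 |
| 60 days | 1.74–1.77 | 0.75–0.76 |

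The daily group gives 1.00 at day 120. If daily use before day 0 lasted only 180 days, the 40-day ranges become 2.00–2.06 and 0.86–0.88. Day 0 itself then reads 1.045, and the daily group reads 1.005 at day 120.

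**Fast distribution phase.** The documents give no values, so these are assumed: 10–50% of the AUC in a phase with a half-life of 0.25–2 days, and a terminal half-life of 40 days.

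| Day 120 is | Single dose | Weekly average |
|---|---|---|
| a dosing day | 1.38–2.01 | 0.59–0.86 |
| a non-dosing day | 2.05–4.05 | 0.88–1.73 |

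The weekly-average error can therefore go either way, depending on a sampling day that the plan does not fix.

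**If the group was already at steady state on three doses a week before day 0.** There is then no shift between the two days. With one compartment, the single-dose reading on a dosing day is about 2.3 times true on both days, and the weekly-average reading is 0.98–0.99. With the same fast phase, the weekly-average reading runs from 0.62 on a dosing day to 2.02 on a non-dosing day.

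**The case against.** The strongest counter-argument concerns reach. CL/F is not one of the substudy's two listed outcomes (SLEDAI-2K change and cytokines). It does not feed the PK-PD model, and no comparison of clearance between days or groups is specifically planned. This is correct and keeps the point small. It does not make the equation valid, and the plan says the parameter will be calculated.

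Second, the two headline factors rest on one compartment, daily dosing before day 0 and a 40-day half-life given for antimalarials as a class. That stands, and the factors should be read with the ranges above. The size moves under other assumptions, but validity is not restored.

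Third, the entry wording could mean that each group was already stable on its own regimen, in which case defining Dose as the weekly average would nearly suffice. That holds only with one compartment. With a fast phase the result still depends on the day sampled.

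Fourth, NONMEM is already in the plan, and a clearance from it will be imprecise with 5 patients per group. Both are true. The first makes the remedy easy, but the stated CL/F equation is still the non-compartmental one. The second is a real cost.

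Fifth, Vd/F has a weakness of its own. Over 24 h the level would fall only 1 − 2^(−1/40) = 1.7%, so a terminal slope can hardly be estimated even in the daily group. That is a further reason not to lean on it.

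**Conclusion.** The concern holds. For the three-times-weekly group at day 120, Dose/AUC0-24 does not estimate CL/F. With true clearance unchanged, daily dosing before day 0, one compartment and a 40-day half-life, it reads about 2 times true with the single dose and about 14% low with the weekly average. Across half-lives of 30 to 60 days the single-dose factor runs from 2.21 down to 1.74. With the assumed fast phase, the overall ranges are 1.38–4.05 and 0.59–1.73.

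Defining Dose removes the interval error in a one-compartment setting but not the steady-state error after a change from daily dosing. The effect is confined to this CL/F, any Vd/F built on it and any comparison that uses them. It should be corrected, but it does not threaten the trial's main comparison.

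**What to change.** In Subproject 1B, Relevant Methods:

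- Limit CL/F = Dose/AUC0-24 to the daily group and to day 0 in patients dosed daily up to then. Do not report it for the three-times-weekly group at day 120, nor at day 0 if that group was already dosed three times a week.
- Keep AUC0-24 in that group as a descriptive exposure measure, and state whether it is taken on a dosing day.
- Take CL/F from the planned NONMEM analysis, using each patient's dosing history and the dosing frequency before day 0.
- Do not report a Vd/F derived from the invalid CL/F, and do not rely on a NONMEM V/F unless the sampling supports it.
- State the dosing frequency before day 0 for both substudy groups.

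This changes analysis wording only and leaves dosing untouched. It needs dose dates and times before the two sampling days, and the earlier dosing frequency, for 10 patients; the only adherence measure described is the MASRI self-report.

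The price is a model-based clearance. It assumes one value per patient over both days, set mainly by day 0, so it is not a test of whether clearance changed. It depends on the recorded doses and will be imprecise. V/F and half-life stay weakly determined: moving the reduced group's AUC ratio from 0.45 to 0.55 moves the implied half-life from about 24 to 53 days. The documents give no sampling times, so whether the planned samples are enough for NONMEM cannot be confirmed.

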ADVANCES IN MECHANISMS Advances in understanding the role of cutaneous HCQ deposes acquired after prolonged previous treatment in maintaining drug-induced TLRs-7 and -9 inhibition would justify reducing the therapeutic dose based on the drug's immunomodulatory mechanisms of action.

SAMPLE SIZE

The sample size was calculated based on the difference in Reactivation of SLE/SJS in one year after the removal or maintenance of hydroxychloroquine, as observed in the study by Tsakonas et al., 1998 and assuming: 95% confidence interval, α error of 5%; power of 80%; expected success rate after 1 year in the group that kept HCQ at the standard dose (Tsakonas et al., 1998)- 84%; expected success rate after 1 year in the group that fully removes HCQ (Tsakonas et al., 1998)- 59%; no-inferiority margin- 50% of the difference between maintaining chloroquine or removing it completely, i.e., delta of 12%; losses- 10%; n in each group- 128; total number of patients to be recruited: 256 (for SLE/JSLE).

statistical analysis The comparison of the risk of inflammatory activity of the disease in patients using standard dose (HCQ 400 mg/day) vs. patients with reduced dose (HCQ 400mg/day - 3X week) will be made through a survival curve by the log-rank test. The categorical variables will be evaluated by fisher's exact or chi-square test and quantitative variables by student and mann-whitney t tests, when applicable.

TITLE OF THE SUBPROJECT 1C

Prospective study of the pharmacokinetics of hydroxychloroquine in patients with Systemic Lupus Erythematosus using attack dose diseases SLE and JSLE.

Justification

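### Subproject 1B asks whether TLR-7/-9 inhibition is maintained on the reduced schedule, but its cytokine objective, test and subgroup cannot show maintenance by dose arm

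*Combined protocol and SAP*

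**What the plan says.** All references are to Subproject 1B of the combined protocol and SAP.

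- **Background.** The closing paragraph gives high importance to finding out whether a lower weekly dose, after long use, "would be able to maintain inhibition of TLR-7 and -9".
- **Advances in Mechanisms.** The subject of the sentence is an advance in understanding what HCQ deposits in the skin contribute. It is this understanding, of their part in "maintaining drug-induced TLRs-7 and -9 inhibition would justify reducing the therapeutic dose", that is expected to support a lower dose.
- **Objectives, secondary.** The entry for this assay is: "Verify a possible longitudinal correlation of HCQ concentrations with the production of interferon-alpha and TNF by plasmacytoid dendritic cells". No objective lists a comparison of cytokine production between the two dose arms.
- **Study Design.** The trial is labelled "Randomized controlled prospective study of non-inferiority of one year of follow-up" in patients in remission. HCQ concentrations are scheduled at entry, 6 and 12 months. For the cytokine assay the text says only: "The production of interferon-alpha and TNF by plasmacytoid dendritic cells will be evaluated in the same period in a subgroup of patients". Further on, the assay material comes from a "random sample of the same number of consecutive patients with active and inactive SLE".
- **Sample Size and statistical analysis.** The plan gives 128 per group with a margin of 12 percentage points on the one-year success rate. Disease activity is analysed by log-rank, categorical variables by Fisher or chi-square, and "quantitative variables by student and mann-whitney t tests, when applicable". No correlation method is named. Cytokine production has no margin, interval rule or sample size.

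**The concern.** Whether inhibition is maintained is a question of no relevant loss. Answering it needs a comparison by randomised arm, an estimate with an interval, and a stated limit on the loss that would still count as maintained. For flares the plan recognises this by setting a margin; for the mechanistic readout it does not.

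Three features leave the question unanswerable as planned:

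1. A correlation between HCQ level and cytokine production describes a concentration relationship. It does not say whether the reduced arm kept its inhibition.
2. A t or Mann-Whitney test takes no difference as its null hypothesis, so failing to reject it is not evidence of no loss.
3. Sampling by active or inactive disease does not secure balance by arm. Because patients enter in remission, active patients can arise only after randomisation, so the subgroup would be selected on something close to the trial's own primary outcome.

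At stake is whether the mechanistic result can properly be cited in support of a lower dose. If a non-significant comparison were taken as maintenance, the claim would become easier to make as the subgroup got smaller.

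**Working it through.** **1. The plan's own figure.** Inputs from Sample Size: success 84% (taken as true in both arms), margin 0.12, power 80%, alpha 5%, losses 10%. With one-sided alpha 0.05:

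n = (1.645 + 0.842)² × 2 × 0.84 × 0.16 / 0.12² = 6.18 × 0.2688 / 0.0144 ≈ 115.4, so 116 per arm.

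Adding 10% gives 116 × 1.10 = 127.6, so 128; dividing by 0.90 gives 129. The stated 128 is reproduced, but it covers the flare endpoint only. No corresponding figure exists for the cytokine assay.

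**2. What a maintenance claim needs, against what is stated.**

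| Needed | Stated in 1B |
|---|---|
| Contrast by randomised dose arm | Correlation with HCQ level |
| Sample drawn by arm, before outcome | Equal numbers active and inactive |
| Stated size | A subgroup, size not given |
| Estimate and interval | Test of difference for quantitative variables |
| Limit on acceptable loss | None for cytokines |
| Entry value as reference | Entry, 6 and 12 months stated for HCQ concentrations; the assay only in the same period |

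**3. Miss rate if non-significance were read as maintenance.** The documents give no subgroup size, SD or effect size, so all three are assumptions and results are in SD units. For n per arm and true loss d (a rise in cytokine production of d SD), the two-sided 5% t test has power P(|T| > t(0.975, 2n−2)), where T is non-central t with 2n−2 degrees of freedom and non-centrality d√(n/2). Miss rate = 1 − power. The 95% half-width is t(0.975, 2n−2) × √(2/n); at n = 20 this is 2.024 × 0.316 = 0.64 SD.

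| n per arm | Miss, d=0.3 | Miss, d=0.5 | Miss, d=0.8 | Miss, d=1.0 | Half-width (SD) |
|---|---|---|---|---|---|
| 10 | 90% | 82% | 61% | 44% | 0.94 |
| 20 | 85% | 66% | 31% | 13% | 0.64 |
| 30 | 79% | 52% | 14% | 3% | 0.52 |
| 40 | 74% | 40% | 6% | 1% | 0.45 |
| 64 | 61% | 20% | 1% | <1% | 0.35 |
| 115 | 38% | 3.5% | <1% | <1% | 0.26 |
| 128 | 33% | 2% | <1% | <1% | 0.25 |

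The row for 115 is 128 less 10% losses (128 × 0.90 = 115.2). The table assumes equal arms and no adjustment for the entry value.

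**4. What a margin-based claim would need.** With no true difference, one-sided 2.5% and 80% power, n per arm = 2 × (1.960 + 0.842)² / m² = 15.70 / m², with m in SD units:

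- m = 0.3: 175 (more than the 128 randomised per arm)
- m = 0.5: 63
- m = 0.8: 25
- m = 1.0: 16

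At one-sided 5% these become 138, 50, 20 and 13. The margins are illustrative; the documents give no basis for choosing one.

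**The case against.** The strongest case against is that the plan never commits to the faulty inference. The sentence about justifying a lower dose sits in an expected-impact section, not in the analysis, and its subject is an advance in understanding. The listed objective is a correlation. The t and Mann-Whitney line is generic and not tied to this assay; given the sampling, its most natural use would be active against inactive patients. Such a test could also be applied to change from entry, so the entry value is not ruled out. The clinical case rests on the flare comparison, which has its own margin.

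Most of this stands. A reader might infer that the plan will declare inhibition maintained because a small subgroup gave a non-significant test. The documents do not support that: no section says how a non-significant result will be read, and the subgroup size is not given, so it cannot be called small. Nor do they support saying that dose reduction depends on this assay.

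The objection does not supply a way to answer the Background question. Neither a correlation nor an active-versus-inactive comparison does so. The PK-PD component does compare two schedules, with plasma TNF-α and IFN-1 as an outcome. However, it has 5 patients per group, and circulating levels are not TLR-stimulated production by plasmacytoid dendritic cells.

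**Conclusion.** The point holds in limited form. Subproject 1B raises a maintenance question and looks to its answer for support, but no listed objective, named method or sampling rule can establish maintenance by dose arm.

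The size is conditional. Were non-significance taken as maintenance, a true 0.5-SD loss would go undetected in about four cases in five at 10 per arm and one in five at 64. If nearly all randomised patients were assayed, the rate would be only 2-4%. Larger losses are missed less often at every size. The figures rest on assumed subgroup and effect sizes and on equal arms, which the stated sampling does not secure.

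The consequence is for supporting mechanistic evidence. The primary flare comparison is not affected by this point.

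**What to change.** In Subproject 1B:

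1. **Sampling (Study Design).** State the assay subgroup size and draw it at entry, stratified by randomised arm. Do not select it on later disease activity.
2. **Schedule.** Confirm that the cytokine assay is done at entry as well as during follow-up.
3. **Analysis.** For each cytokine and each agonist, model log production during follow-up on randomised arm, adjusted for the patient's entry value. Report the reduced/standard ratio with its 95% interval.
4. **Inference.** State that a non-significant t or Mann-Whitney test is not evidence of maintenance. Use the word maintained only if the upper bound of the ratio lies below a margin fixed before the assay results are seen by arm.
5. **If no margin is set.** Label the result exploratory and soften the sentence in Advances in Mechanisms.

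Items 3 to 5 cost plan wording and a standard covariance analysis. Items 1 and 2 may cost more: entry samples must be collected and processed for the chosen patients if that is not already planned. The main drawback is that a small subgroup will often be inconclusive (at 20 per arm the unadjusted interval is about ±0.64 SD), and the report must then say so.
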